# Issue 2: Is the endpoint appropriately analyzed using ordinary survival analysis or competing risks survival analysis?

For this issue, we consider use of a time-to-event method to assess vaccine efficacy. In general, a competing risk of a given endpoint of interest is an endpoint that, once it occurs, precludes the possibility of future occurrence of the other endpoint.

- 1. COVID is a competing risk for asymptomatic infection
- 2. Severe COVID is a competing risk for non-severe COVID

Therefore, the asymptomatic infection and non-severe COVID endpoints may be best analyzed by competing risks methods. For example, instead of estimating cumulative incidence  $P(T \le t | A = a)$  for a given randomization arm A = a, where T is the time from enrollment until the endpoint, we analyze cumulative incidence  $P(T \le t, J = 1 | A = a)$ , where T is the time to the first event of J = 1 (event of interest) or J = 2 (competing event), and cumulative VE(t) may be assessed using the parameter

$$VE(t) = 1 - \frac{P(T \le t, J = 1 | A = 1)}{P(T \le t, J = 1 | A = 0)}.$$

In addition, hazard-ratio-based VE may be defined as one minus the cause (J = 1)-specific hazard ratio (Prentice et al., 1978; Gilbert, 2000).

It is also worth noting that:

- 1. Asymptomatic infection is not a competing risk for COVID, because participants experiencing the asymptomatic infection endpoint continue follow-up for the COVID endpoint (such that at asymptomatic infection diagnosis it is not known whether the infection is truly asymptomatic or pre-symptomatic), and it is not certain that seroconversion prevents future COVID (if future knowledge supports this conclusion, then asymptomatic infection could be treated as a competing risk).
- 2. Non-severe COVID is not a competing risk for severe COVID. At presentation, if the COVID event does not qualify as severe, then post-COVID diagnosis follow-up is required to determine whether the endpoint registers as non-severe or severe. One will only know the endpoint is not severe after post-COVID diagnosis follow-up is completed (symptoms resolve), such that the failure time is not known until the end of post COVID diagnosis follow-up. Therefore, non-severe COVID is not a competing risk for severe COVID, and the severe COVID endpoint can be analyzed using ordinary survival analysis ignoring the non-severe COVID endpoint.

In sum, the COV-INF, COVID, and severe COVID endpoints will be analyzed by ordinary survival analysis methods, whereas the asymptomatic infection and non-severe COVID endpoints will be analyzed using competing risks methods. Moreover, adding nomenclature precision, for the parent infection endpoint, the daughter endpoints COVID and asymptomatic infection are semi-competing risks data (nomenclature in the survival analysis literature), and for the COVID parent endpoint, the daughter endpoints severe COVID and non-severe COVID are semi-competing risks data.

In addition, one non-clinical endpoint may be important for correlates assessment: SARS-CoV-2 viral load at COVID diagnosis (VL Dx) (e.g., measured by nasal swab), or alternatively area under the viral load curve (AUC-VL) from the COVID diagnosis date through to undetectable viral load, or to an alternative threshold indicating low viral load. Viral load endpoints are putative surrogates of disease progression and severity for the individual, and are also putative surrogates for secondary transmission; moreover the quantitative nature of viral load endpoints may afford an opportunity to increase statistical power.

#### Issue 3: Coarseness level of the failure time variable

- 1. **COVID:** Event time defined in 'continuous time' on the day of virological confirmation.
- 2. Asymptomatic infection: Event time defined only at fixed infrequent visits (e.g., Month 6, 12, 18, 24).
- 3. **COV-INF:** Event time defined as 'mixed continuous and discrete', equal to the day of virological confirmation (if COVID) and by the first sero-postive visit (if asymptomatic infection).
- 4. Non-severe COVID: Event time may be defined in continuous time, as the number of days from enrollment to COVID diagnosis plus the number of additional days until the COVID event is known to be non-severe. However, following the decision made for Issue 1, we simplify and define the event time at COVID diagnosis.
- 5. Severe COVID: Event time may be defined in continuous time, as the number of days from enrollment to COVID diagnosis plus the number

of additional days until the COVID event is known to be severe (which may be zero days). However, following the decision made for Issue 1, we simplify and define the event time at COVID diagnosis.

#### Issue 4: Binary endpoint vs. failure time endpoint

In general, in phase 3 trials with prospective follow-up for event occurrence where right-censoring occurs (either due to administrative censoring or loss to follow-up), it can be advantageous to conduct data analysis in a survival analysis paradigm. Many of the correlates analyses are specified as such. However, because the endpoints are rare, and the rate of loss to follow-up is anticipated to be very low, reliable and interpretable answers may be obtained based on simpler methods that use binary endpoints, and deal with loss to follow-up in a cruder way. If retention is very high, such that bias and precision may be minimally impacted by use of a binary endpoint, some of the correlates analyses may use a binary endpoint. In settings with competing risks, such analyses would treat the endpoint as multinomial and utilize methodology accordingly.

In sum, correlates methods are needed that consider time-to-event or binary endpoints, with or without accounting for a competing risk. In addition, the methods need to be able to handle continuous, discrete, and mixed continuous/discrete failure times.

#### 8 Case-cohort Sampling Design for Measuring Antibody Markers

Figure 3 illustrates the case-cohort (Prentice, 1986) sampling design that is used for measuring Day 1, 57 antibody markers (and the later time points at a later point in time) in a random sample of trial participants. The random sample is stratified by the key baseline covariates: assigned randomization arm, baseline SARS-CoV-2 status (defined by serostatus and possibly also NAAT and/or RNA PCR testing), any additional important demographic factors such as the randomization strata (e.g., defined by age and/or comorbidities), and underrepresented minority status within the U.S. Because the design uses a stratified random sample instead of the simple random sample proposed by Prentice (1986), the design may also be referred to as a "two-phase sampling design" (Breslow et al., 2009b,a), where "phase one" refers to variables measured in all participants and "phase two" refers to variables only measured in a subset (thus the "case-cohort sample" constitutes the phase-two data).

The case-cohort design enables obtaining marker data (Day 1, 57) for the immunogenicity subcohort during early trial follow-up in real-time batches, thereby accelerating the time until final data set creation and hence data analysis and results on Day 57 marker correlates. The design allows using the same immunogenicity subcohort to assess correlates for multiple endpoints, relevant for the COVID-19 VE trials with multiple endpoints (Figure 1). This makes the design operationally simpler than a case-control sampling design.

#### 8.1 Prototype USG COVID-19 Response Team immunogenicity subcohort

Table 5 summarizes the size of the prototype USG COVID-19 Response Team immunogenicity subcohort, by baseline factors used to stratify the random sampling. In this subcohort 6 baseline demographic strata are used; if a trial has a different number of baseline demographic strata, then the table would be modified, holding the total sample size of the subcohort approximately fixed. For U.S. strata, all USG COVID-19 Response Team trials specify 50:50 balance by underrepresented minority status Yes:No. The subcohort sampling is implemented to create representative sampling across the entire period of enrollment. Non-USG COVID-19 Response Team trial sampling designs would likely be similar, with different baseline sampling strata perhaps even the simplest case with no sampling strata and use of simple random sampling. 'At-risk' refers to participants considered to be at heightened risk of severe COVID-19 illness based on a specified list of conditions.
Table 5: Planned Immunogenicity Subcohort Sample Sizes by Baseline Strata for Antibody Marker Measurement

	Baseline SARS-CoV-2 Negative 							Baseline SARS-CoV-2 $Positive^3$					
Bas. Cov. Strata 	1	2	3	4	5	6	1	2	3	4	5	6	
Vaccine	150	150	150	150	150	150	50	50	50	50	50	50	
Placebo	20	20	20	20	20	20	50	50	50	50	50	50	

This schema specifies 6 baseline covariate strata for stratified sampling, for example 1 = U.S. Age 18-64 Minority; 2 = U.S. Age 18-64 non-Minority; 3 = U.S. Age  $\geq 65$  Minority;

 $4 = U.S \text{ Age} \ge 65 \text{ non-Minority}; 5 = \text{non-U.S. Age } 18-64; 6 = \text{non-U.S. Age} \ge 65.$ 

The vaccine group baseline negative strata are assigned large sample sizes because the correlates of risk analysis focuses on baseline negative vaccine recipients. The placebo group baseline negative strata are assigned small sample sizes given the expectation that almost all Day 57 bAb and nAb readouts

will be negative/zero given the absence of prior exposure to SARS-CoV-2 antigens. Equal stratum sizes are assigned for the vaccine and placebo groups in order to compare bAb and nAb responses in previously infected persons, studying potential differences in natural+vaccine-elicited responses vs. natural-elicited responses.

If certain strata do not have enough eligible participants available for sampling, then additional sampling is done from other strata to keep the total immunogenicity subcohort sample size to close to 1620. A separate USG COVID-19 Response Team Antibody Marker sampling plan describes the algorithm, available upon request.

#### 8.1.1 Additional sampling of participants missing the second dose

For trials with two doses of vaccine, the set of baseline negative strata for vaccine recipients is expanded to also include the subgroup that misses the second vaccination and minimally has available samples at Day 57, and similarly the corresponding subgroup to placebo recipients is added; these subgroups are defined regardless of baseline demographic factors. For the vaccine subgroup, a random sample of 150 (or the number available, whichever is smaller) participants is sampled, and for the placebo subgroup, a random sample of 20 (or the number available, whichever is smaller) participants is sampled. This additional sample may not be drawn until the last participant reaches 1 or 2 years of follow-up, to be able to ensure that sampled participants have many samples available. The two objectives of the additional sampling are: (1) To compare long-term antibody responses one dose vs. two doses; and (2) to increase power of the Stage 2 analysis of outcome-proximal correlates.

#### 8.2 Correlates Objectives Addressed in Two Stages

Figure 4 depicts the two stages of the immune correlates analyses. Stage 1 includes antibody marker data from all COVID and COV-INF cases diagnosed through to the last date of: (1) the time that at least 25 evaluable vaccine breakthrough COVID endpoint cases are available for analysis; and (2) the time of a data-cut at or after the primary analysis used to define the data base for the first correlates analysis. Only Day 1, 57 antibody markers, and COVID and COV-INF diagnosis time point antibody markers, are measured in Stage 1. The objectives of Stage 1 correlates analyses focus on Day 57 markers, which are the objectives listed in Table 1. Stage 1 focuses on Day 57 markers because in general validated or non-validated surrogate endpoints for approved vaccines are based on the peak antibody time point, and this approach fits the priority to develop a validated or non-validated surrogate endpoint as rapidly as possible.

Stage 2 includes antibody marker data from all COVID and COV-INF cases diagnosed after the Stage 1 cases through to the end of the trial, including all available sampling time points (6–7 time points). For immunogenicity subcohort participants, the antibody markers at all available time points other than Day 1, 57 are measured for Stage 2 correlates analyses (4–5 additional time points). The Stage 2 clinical endpoint data and antibody marker data enable assessment of longitudinal antibody markers as outcome-proximal correlates of instantaneous endpoint risk and as various types of outcome-proximal correlates of protection.

The Stage 1 immunogenicity subcohort sampling plan is finalized prior to or shortly after study start. The Stage 2 sampling plan is not made until after the results on vaccine efficacy at the primary analysis are known. The Study Oversight Group may modify the scope of the set of samples for immunoassay measurements in Stage 2 based on analysis results. The essential distinguishing mark of Stage 1 vs. Stage 2 is assessment of Day 57 marker correlates that can be done using antibody data only from Day 1, 57 markers vs. assessment of outcome-proximal correlates that requires antibody data longitudinally including at endpoint diagnosis dates.

# 8.2.1 Prioritize antibody marker measurement at COVID and COV-INF diagnosis sampling time points

Conduct of the immunologic assays on diagnosis date samples for all COVID and all COV-INF endpoint samples is of the highest priority, equal to the priority of conducting the assays on the Day 1, 57 samples.

#### 8.2.2 [With Day 29 markers]

Moreover, if Day 29 markers are included, then Stage 1 also focuses on Day 29 markers because if a correlate based on this time point is found to perform as well as a Day 57 correlate, then it may be preferred given the practical advantage to be measured earlier and to not require a Day 57 post-vaccination visit and blood draw. Another advantage of an earlier measurement is providing opportunity to include additional breakthrough COVID endpoint cases (intercurrent endpoints) in the correlates analyses.

# 9 Unsupervised Feature Engineering of Antibody Markers (Stage 1: Day 1, 57)

#### 9.1 Descriptive Tables and Graphics

#### 9.1.1 Antibody marker data

Binding antibody titers to full length SARS-CoV-2 Spike protein, to the RBD domain of the Spike protein, and to the Nucleocapsid (N) protein will be measured in all participants in the immunogenicity subcohort (augmented with infected cases). N-specific binding antibody titers are not used for correlates analyses or for graphical reporting; these data are only used for tabular reporting. Binding antibody IgG Spike, IgG RBD, IgG N, as well as fold-rise in these three markers from baseline, are measured at each pre-defined time point. Indicators of 2-fold rise and 4-fold rise in IgG concentration (fold rise [post/pre]  $\geq 2$  and  $\geq 4$ , 2FR and 4FR) are measured at each pre-defined

post-vaccination timepoint. Binding antibody responders to a given antigen at each pre-defined timepoint are defined as participants with value above the antigen-specific positivity cut-off. Binding antibody IgG 2FR (4FR) at each pre-defined timepoint to a given antigen are defined as participants who had baseline values below the LLOQ with IgG concentration at least 2 times (4 times) above the assay LLOQ, or as participants with baseline values above the LLOQ with at least a 2-fold (4-fold) increase in IgG concentration.

Pseudovirus neutralizing antibody ID50 and cID80 titers, as well as fold-rise in ID50 and cID80 titers from baseline, are measured at each pre-defined time point. Indicators of 2-fold rise and 4-fold rise in ID50 titer (fold rise  $[post/pre] \ge 2$  and  $\ge 4$ , 2FR and 4FR) are measured at each pre-defined post-vaccination timepoint.

Neutralization responders at each pre-defined timepoint are defined as participants who had baseline values below the LLOD with detectable ID50 neutralization titer above the assay LLOD, or as participants with baseline values above the LLOD with a 4-fold increase in neutralizing antibody titer. Neutralization 2FR (4FR) at each pre-defined timepoint are defined as participants who had baseline values below the LLOQ with ID50 at least 2 times (4 times) above the assay LLOQ, or as participants with baseline values above the LLOQ with at least a 2-fold (4-fold) increase in neutralizing antibody titer. While quantitative fold-rise is shown for both ID50 and cID80, response above LLOD, 2FR and 4FR responder status are shown only for ID50. (However, for superlearner analysis of multivariable CoRs, 2FR and 4FR responder status variables are included for each of pseudovirus-nAb ID50 and cID80, given the objectives of more comprehensive analysis in building the estimated optimal surrogate.)

For WT live virus-nAb MN50, the same types of variables are analyzed/reported as for pseudovirus-nAb ID50.

Note that for defining positive response, 2FR, and 4FR, a reason why values below the LLOD are set to half the LLOD before calculating the indicator of response, is to ensure that a vaccine recipient that has an unusually low antibody readout at baseline and a post-vaccination value below or near the LLOD is not erroneously counted as a responder.

The following list describes the antibody variables that are measured from immunogenicity subcohort and infection case participants.

- 1. Individual anti-Spike antibody concentration at each pre-defined time point
- 2. Individual anti-Spike antibody fold-rise concentration post-vaccination relative to baseline at each pre-defined post-vaccination time point
- 3. Individual anti-RBD antibody concentration at each pre-defined time point
- 4. Individual anti-RBD antibody fold-rise post-vaccination relative to baseline at each pre-defined post-vaccination time point
- 5. Individual anti-N antibody concentration at each pre-defined time point
- 6. Individual anti-N antibody fold-rise post-vaccination relative to baseline at each pre-defined post-vaccination time point
- 7. 2-fold-rise and 4-fold rise (fold rise in anti-Spike antibody concentration [post/pre]  $\geq$  2 and  $\geq$  4, 2FR and 4FR) at each pre-defined postvaccination time point
- 8. 2-fold-rise and 4-fold rise (fold rise in anti-RBD antibody concentration [post/pre]  $\geq$  2 and  $\geq$  4, 2FR and 4FR) at each pre-defined postvaccination time point
- 9. 2-fold-rise and 4-fold rise (fold rise in anti-N antibody concentration  $[post/pre] \ge 2$  and  $\ge 4$ , 2FR and 4FR) at each pre-defined post-vaccination time point
- 10. Pseudovirus-nAb responders, at each pre-defined timepoint defined as participants who had baseline values below the LLOQ with detectable pseudovirus-nAb ID50 titers above the assay LLOQ or as participants with baseline values above the LLOQ with a 4-fold increase in pseudovirus-nAb ID50 titers
- 11. Wild type live-virus-nAb responders, at each pre-defined timepoint de-

fined as participants who had baseline values below the LLOQ with detectable WT live virus-nAb MN50 titers above the assay LLOQ or as participants with baseline values above the LLOQ with a 4-fold increase in WT live virus-nAb MN50 titers

Summaries of the immunogenicity data will be reported in tables. In particular, the tables will include, for each pre-defined post-baseline time point:

1. For each binding antibody marker, the estimated percentage of participants defined as responders, and with concentrations  $\geq 2x$  LLOQ or  $\geq 4 \times LLOQ$ , will be provided with the corresponding 95% CIs using the Clopper-Pearson method.

In addition, the estimated percentage of participants defined as responders, participants with 2-fold rise (2FR), and participants with 4-fold rise (4FR) will be provided with the corresponding 95% CIs using the Clopper-Pearson method.

- 2. For the ID50 pseudo-virus neutralization antibody marker, the estimated percentage of participants defined as responders, participants with 2-fold rise (2FR), and participants with 4-fold rise (4FR) will be provided with the corresponding 95% CIs using the Clopper-Pearson method
- 3. For the MN50 WT live virus neutralization antibody marker, the estimated percentage of participants defined as responders, participants with 2-fold rise (2FR), and participants with 4-fold rise (4FR) will be provided with the corresponding 95% CIs using the Clopper-Pearson method
- 4. Geometric mean titers (GMTs) and geometric mean concentrations (GMCs) will be summarized along with their 95% CIs using the t-distribution approximation of log-transformed concentrations/titers (for each of the 5 Spike-targeted marker types including pseudovirus-nAb ID50 and cID80 and WT live virus-nAb MN50, as well as for binding Ab to N).
- 5. Geometric mean titer ratios (GMTRs) or geometric mean concentration ratios (GMCRs) are defined as geometric mean of individual titers/concentration ratios (post-vaccination/pre-vaccination for each injection)
- 6. GMTRs/GMCRs will be summarized with 95% CI (t-distribution ap-

proximation) for any post-baseline values compared to baseline, and post-Day 57 values compared to Day 57

- 7. The ratios of GMTs/GMCs will be estimated between groups with the two-sided 95% CIs calculated using t-distribution approximation of log-transformed titers/concentrations [the groups compared are vaccine recipient Non-Cases vs. vaccine recipient breakthrough cases used for Day 57 marker correlates analyses (Primary cases) and vaccine recipient Non-Cases vs. vaccine recipient breakthrough cases used for Day 29 marker correlates analyses (Intercurrent cases and Primary cases)].
- 8. The differences in the responder rates, 2FRs, 4FRs between groups will be computed along with the two-sided 95% CIs by the Wilson-Score method without continuity correction (Newcombe, 1998) (the groups for comparison are as described in the previous bullet).

All of the above point and confidence interval estimates will use inverse probability of antibody marker sampling weighting in order that estimates and inferences are for the population from which the whole study cohort was drawn. In two-phase sampling data analysis nomenclature, the "phase 1 ptids" are the per-protocol individuals excluding individuals with a COVID failure event or any other evidence of SARS-CoV-2 infection < 7 days post Day 57 visit. The "phase 2 ptids" are then the subset of these phase 1 ptids in the immunogenicity subcohort with Day 1 and 57 Ab marker data available. Thus, marker data for the COVID endpoint cases outside the subcohort will not be used in immunogenicity analyses; these cases are excluded from immunogenicity analyses. Thus again, marker data for the COVID endpoint cases outside the subcohort will not be used in immunogenicity analyses; these cases are excluded from immunogenicity analyses.

other Race subgroups are defined solely by the Race variable, with levels Black, Asian, American

Indian or Alaska Native, Native Hawaiian or Other Pacific Islander, Multiracial, Other, Not reported, Unknown.

For comparing antibody levels between groups, the following groups are compared:

- Baseline negative vaccine vs. baseline negative placebo
- Baseline positive vaccine vs. baseline positive placebo
- Baseline negative vaccine vs. baseline positive vaccine
- Within baseline negative vaccine recipients, compare each of the following pairs of subgroups listed in Table 6: Age ≥ 65 vs. age < 65; risk for severe COVID: at risk vs. not at risk; age ≥ 65 at risk vs. age ≥ 65 not at risk; age < 65 at risk vs. age < 65 not at risk; male vs. female; Hispanic or Latino ethnicity: Hispanic or Latino vs. Not Hispanic or Latino; Underrepresented minority status: Communities of color vs. White non-Hispanic (within the U.S.).

The entire immunogenicity analysis is done in the per-protocol cohort with both Day 1 and Day 57 marker data available (the two-phase sample).

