$$\begin{split} \rho[i,j] &= 0.55 + 0.1I(i=3, j=4) + 0.2 * I(i=5, j=6) : i=1, \cdots, 6, j > i \\ \rho[i,j] &= 0.6 + 0.1I(i=8, j=9) + 0.2 * I(i=10, j=11) : i=7, \cdots, 11, j > i \\ \rho[i,j] &= 0.7 + 0.1I(i=13, j=14) + 0.2 * I(i=15, j=16) : i=12, \cdots, 16, j > i \end{split}$$

In the above correlation specification, note that extra correlation is added to IgG Spike and RBD readouts (same assay), as well as to PsV ID50 and cID80 (same assay). After  $\rho[i, j]$  is define for all i < j, we set  $\rho[j, i] = \rho[i, j]$ for all j < i.

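### Section 9.1.1 assigns no estimator to the baseline-positive vaccine versus placebo antibody comparison, and its only between-group ratio method would leave the Day 1 value unused

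*Combined protocol and SAP*

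**What the plan says.** After Table 6, SAP Section 9.1.1 lists the groups whose antibody levels are compared, including "Baseline positive vaccine vs. baseline positive placebo". No method is given there.

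The sample was sized with this pair in mind. Footnote 3 to Table 5 (Section 8.1) explains: "Equal stratum sizes are assigned for the vaccine and placebo groups in order to compare bAb and nAb responses in previously infected persons".

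The between-group method comes earlier in Section 9.1.1, as item 7 of the table contents: "The ratios of GMTs/GMCs will be estimated between groups with the two-sided 95% CIs calculated using t-distribution approximation of log-transformed titers/concentrations". No covariate is named. The bracket that follows fixes the groups: "the groups compared are vaccine recipient Non-Cases vs. vaccine recipient breakthrough cases used for Day 57 marker correlates analyses (Primary cases"), with a second case/non-case pair for Day 29. Item 8, on differences in response rates, uses the same groups. The text after item 8 adds inverse probability of sampling (IPS) weights.

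On availability of baseline values, Section 9.1.1 says: "The entire immunogenicity analysis is done in the per-protocol cohort with both Day 1 and Day 57 marker data available".

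Within the immunogenicity analysis, Day 1 enters through geometric mean fold-rises (items 5 and 6), the 2-fold, 4-fold and neutralisation responder indicators, and the Day 1 and delta plots and correlations of Section 9.1.3. No between-arm ratio of fold-rises and no model containing Day 1 is specified.

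**The concern.** Two things are unsettled. First, the listed comparisons and the ratio method do not match: the list names arms, serostatus groups and demographic subgroups, while item 7 names cases and non-cases. An analyst must guess how the vaccine versus placebo ratio is to be computed.

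Second, the natural guess is to carry item 7 over to this pair, which gives an unadjusted ratio. In baseline-negative participants little would be lost, since Day 1 readouts are expected to be mostly negative. Baseline-positive participants differ: the mock-data defaults in Section 24.2.1 give them Day 1 SDs of 0.6 to 0.8 log10. If Day 1 predicts Day 57, omitting it widens the interval for the vaccine's effect on antibody in previously infected people and leaves any chance Day 1 imbalance between the sampled arms in the estimate. Section 19 recognises the principle for vaccine efficacy in baseline positives, where it treats Day 1 markers as a baseline covariate suitable for regression.

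**Working it through.** **Sample size.** Table 5 gives 6 × (150 + 20 + 50 + 50) = 1620, matching the stated total. The baseline-positive part is 6 × 50 = 300 per arm, 600 in all. The SAP states no precision figure for this comparison, so there is none to reproduce.

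**Correlation.** Section 24.2.1 orders the simulated variables as age, BMI, five Day 1 markers (positions 3–7), five Day 29 markers (8–12) and five Day 57 markers (13–17). In both baseline-positive groups the first rows have correlation "0.55 + 0.1I(i=3, j=4) + 0.2 * I(i=5, j=6") for i from 1 to 6 and j above i. The same-marker Day 1 to Day 57 correlation is therefore 0.55 for Spike, RBD, ID50 and ID80. MN50 (i = 7) falls under the next line, at 0.60.

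**SDs.** The Day 57 defaults for the baseline-positive vaccine group are 0.8, 0.8, 0.8, 0.98 and 0.94 log10. The placebo list is one entry short as printed, so I use the vaccine values in both arms.

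**Variance.** With correlation ρ, equal in both arms, variance adjusted for Day 1 ÷ unadjusted variance = 1 − ρ². The log-scale interval width scales with √(1 − ρ²).

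| ρ | Variance reduction | Interval narrower by |
|---|---|---|
| 0.3 | 9% | 5% |
| 0.4 | 16% | 8% |
| 0.55 (default) | 30% | 16% |
| 0.60 (default, MN50) | 36% | 20% |
| 0.7 | 49% | 29% |

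A simulation at ρ = 0.55 with 300 per arm (4,000 replicates) gave a variance ratio of 0.716, close to the theoretical 0.6975. In sample-size terms, 300 ÷ 0.6975 = 430 per arm unadjusted.

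**Interval for the ratio.** Multiplier = 10^(1.96 × SD × √(2/300)), with the exponent multiplied by √(1 − ρ²) after adjustment.

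- SD 0.8, ρ 0.55: 10^0.128 = 1.34, falling to 10^0.107 = 1.28.
- SD 0.98 (ID80), ρ 0.55: 10^0.157 = 1.44, falling to 10^0.131 = 1.35.
- SD 0.94 (MN50), ρ 0.60: 10^0.150 = 1.41, falling to 10^0.120 = 1.32.

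These ignore the design effect of the sampling weights, so the actual intervals will differ.

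**Fold-rise instead.** A between-arm fold-rise contrast would have variance s57² + s1² − 2ρ·s1·s57, where s1 and s57 are the Day 1 and Day 57 SDs. For Spike this is 0.64 + 0.36 − 0.528 = 0.472 against 0.64, a 26% reduction. The others are RBD 20%, ID50 10%, ID80 23% and MN50 30%. This recovers part of the gain, but the SAP does not specify the contrast.

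**The case against.** The strongest objection is textual. A reader might infer that the SAP has chosen an unadjusted ratio for this pair. It has not said so: item 7 is tied to case/non-case groups and the list of pairs names no estimator. That stands, and the point is therefore an unspecified estimator whose nearest template has no covariate.

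A reader might also take 30% as the SAP's own estimate of the loss. The 0.55 is a default for generating mock data, one constant applied to nearly every pair in those rows, including age with BMI. Baseline positivity may also rest on NAAT or PCR (Section 8), so some participants could have low Day 1 antibody and the true correlation could be smaller. Under the same matrix age alone explains 30% of Day 57 variance, and Day 1 would then remove about a further 13% of what remains (18% for MN50). All of this stands as a limit on the size. It does not remove the gain over an analysis that adjusts for neither; age and Day 1 together would explain 2 × 0.3025 ÷ 1.55 = 39%.

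Translating the gain into power is tempting too. The SAP attaches no test or power target to this comparison, and Section 3.1 describes baseline-positive data as immunogenicity characterisation. No power claim is warranted.

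Finally, the set is per-protocol and excludes early infections, so the comparison rests on randomisation without being strictly randomised. The weights are computed within arm, serostatus and demographic stratum, so the strata are not ignored, and fold-rise summaries already use Day 1 within arm. These points are correct, but none of them is a baseline-adjusted between-arm estimate.

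**Conclusion.** The point holds as a specification gap with an inexpensive gain in efficiency. The estimator for the baseline-positive vaccine versus placebo ratio needs stating, and the item 7 groups do not match the listed comparisons. If item 7 is carried over, the ratio is unbiased as far as the documents show but less precise than the data allow. The illustrative loss at the mock-data default is about 30% of variance, or 16% of log-scale interval width, with a range of 9% to 49% of variance for correlations of 0.3 to 0.7. This assumes equal correlation and SD in the two arms, the full 300 per arm, and a weighting design effect common to both analyses. The actual size will be visible from the trial, because Section 9.1.3 already plans to describe the Day 1 to Day 57 correlation by arm and baseline status. The documents do not support a claim of bias, or of power lost on a planned test. The correlates analyses are unaffected.

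**What to change.** In Section 9.1.1, state the estimator for each pair in the comparison list and correct the group list in item 7 (and item 8, which refers back to it).

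For baseline-positive vaccine versus placebo, estimate the Day 57 GMT/GMC ratio by IPS-weighted linear regression of the log10 marker on arm, log10 Day 1 value of the same marker and the demographic sampling strata, with design-based standard errors. Report the back-transformed arm coefficient as the main estimate and keep the unadjusted ratio as descriptive. Do the same at Day 29 if those markers are included. Leave the baseline-negative versus baseline-positive comparison unadjusted, because Day 1 differs between those groups by definition.

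The cost is a few lines of SAP text and one weighted regression per marker and time point, on data the analysis set already requires.
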